7.2 General Methodology

The data from control group and treatment group will be evaluated independently for all endpoints. Also, Cohort A and Cohort B will be analysed independently.

Summary statistics for Continuous variables will be represented by number of subjects(n), mean, median, standard deviation, minimum and maximum and categorical variables will be represented by counts and percentages. P-values for hypothesis testing will be evaluated based on two-sided testing using significance level of 0.05. Confidence intervals will be reported as two-sided 95% confidence intervals. For comparison of primary, secondary, and ancillary endpoints, normality will be verified for appropriate statistical methodology. Comparisons between the study phase and the continuation phase will be performed using a paired T-test for testing the statistical significance of the difference in continuous variables if normality assumption is met or Wilcoxon signed rank test in continuous variables if normality assumption is not met.

The templates for Tables, Listings and Figures (TLFs) will be available in the TLFs document.

7.3 Center Pooling

Data will be pooled for exploratory analysis.

7.4 Handling of Missing, Unused, and Spurious Data and Dropouts

Data entry error or non-reasonable values will be resolved before data analysis. No imputations will be done for missing data. Analysis will be done by all available data.

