9.6. Early Termination Visit

Whenever possible, the study staff will perform an Early Termination visit when a subject decides to withdraw from the study early or if the subject is withdrawn early upon decision of investigator (during a normal study visit or an unscheduled visit). This visit can be conducted onsite or remotely.

Early Termination procedures:

- Upload AHCL pump into CareLink. Use correct Subject ID (327-XXX-XXX).
- Subject to complete questionnaires HFS, DTSQs, DTSQc and DQoL, if possible.
- Collect blood sample for HbA1c (central lab kit), if possible.
- Review adverse event or device deficiency, if any.
- Collect all study supplies back from subjects.

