4.1.2 Objective for Treatment Group

The primary objective is to confirm the long-term benefits of AHCL therapy. The non-inferiority on glycemic control of the AHCL system in continuation phase versus in study period will be tested.

5. Investigation Plan

This study is a pre-market, multi-center, prospective, open label, adaptative, confirmatory, randomized controlled trial in insulin-requiring adult subjects with type 1 diabetes on MDI therapy. The study period for each subject will be approximately 13 months.

Figure 1: Study Design

The study consists of two separate cohorts, Cohort A with subjects on MDI + FGM (confirmatory part of the study) and Cohort B with Subjects on MDI + Real-Time CGM (exploratory part of the study). Each cohort will have a separate randomization.

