6.2 Sample Size Considerations for Study Period

For Cohort A (MDI+FGM), the sample size calculation was performed based on the following assumptions: alpha=0.05, power=80%, 0.7 standard deviation and 0.5 reduction in mean change of HbA1c in the treatment arm, as compared to the control arm, which is the minimum clinically meaning difference. The standard deviation was based on the *Eurythmics study* (Hermanides, 2011) comparing SAP therapy (Treatment arm) vs MDI (control arm) with a pooled standard deviation of 0.83.

Based on these assumptions, the minimum sample size required is 64 subjects (32 in each arm) in Cohort A comparing AHCL with MDI + FGM subjects.

The following drop-out assumptions have been taken into account, based on experience with previous studies: At screening: 10%; After run-in: 5%; During 6-month follow-up: 7.5%.

Incorporating these drop-out rates, a total of 84 subjects need to be screened in Cohort A (AHCL vs MDI+FGM) in order to have 74 subjects starting the run-in phase, 70 subjects randomized to start the treatment phase and 64 subjects to complete the study phase (6 months). To minimize imbalance in the number of subjects across sites, a minimum of 4 and a maximum of 20 subjects of the cohort should be randomized at each site, with the current sample size.

For the exploratory analysis in Cohort B, comparing MDI + CGM versus AHCL, 30 subjects will be required for analysis. Incorporating the expected dropout rates, a total of 40 subjects need to be screened, in order to have 36 subjects starting the run-in phase, 34 subjects randomized to start the treatment phase and 30 subjects to complete the study. Subjects will be randomized in a 1:1 ratio to the 2 arms.

7. Statistical Methods

The methods in this section are applicable to cohort A and cohort B in continuation phase. The analysis is focused on comparing the therapy outcomes of control group between the study period and continuation phase in cohort A. Similar analysis for treatment group will be conducted as well. These methods are also applicable to cohort B.

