7.1.3 Analysis Sets

7.1.3.1 Efficacy analysis set

For the primary, secondary and ancillary endpoints efficacy analyses will be performed in the Intent to Treat (ITT) basis. The ITT set will be composed of all subjects who entered the continuation phase.

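### The continuation-phase HbA1c non-inferiority test drops subjects in the ITT set who have no Visit 13 value, departs from the protocol's mixed model, and would favour non-inferiority if leavers do worse

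*SAP*

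**What the plan says.** The SAP covers the continuation phase and declares all its analyses exploratory and unpowered (opening of section 4, section 6). For the treatment group, SAP 4.1.2 says: "The primary objective is to confirm the long-term benefits of AHCL therapy". SAP 7.5.2 and 7.9.2.1 turn this into a non-inferiority test of mean HbA1c at Visit 13 against Visit 8, with a margin of 0.3%. The test is a paired t test, or a Wilcoxon signed rank test if normality is rejected. It is the first step of a fixed sequence; the five sensor-glucose steps are reached only if it succeeds. (SAP 7.9.2.1 names the control group in several places although it sits under the treatment-group heading. It is read here as meaning the treatment group, and that text needs reconciling.)

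On the analysis set, SAP 7.1.3.1 says: "The ITT set will be composed of all subjects who entered the continuation phase". On missing data, SAP 7.4 says: "No imputations will be done for missing data. Analysis will be done by all available data".

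The protocol differs in three respects. Section 13.6 calls for a linear mixed model for endpoints with repeated measures, and section 5.3.3 lists HbA1c change to 12 months as an ancillary endpoint. Section 9.6 provides for an early-termination sample: "Collect blood sample for HbA1c (central lab kit), if possible". By the footnotes to Tables 5 and 6, that visit applies to any withdrawal between randomization and Visit 13. Section 13.7 plans sensitivity analyses for missing HbA1c, but only at 3 and 6 months.

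**The concern.** A paired test uses only subjects with both values. For this endpoint, the ITT label and the promise to use the available data do not describe what the test does. The Visit 8 value of an entrant without Visit 13 goes unused, and the SAP gives an early-termination HbA1c no role.

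This matters because the question is whether the benefit lasts. The protocol gives reasons why exits might be related to control. Participants who miss arranged contacts may be discontinued (9.1). Subjects may be removed for not meeting study requirements, and those who leave return the devices and go back to routine care (9.14). If such subjects would have had a larger HbA1c rise than completers, omitting them lowers the estimated rise. For a non-inferiority test that is the anti-conservative direction, and the test in question decides whether the rest of the hierarchy is reached.

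**Working it through.** **The plan's own figure.** The continuation phase has no stated N, power or dropout rate. The only sizing is for the Cohort A study phase (SAP 6.2): "alpha=0.05, power=80%, 0.7 standard deviation and 0.5 reduction in mean change of HbA1c in the treatment arm". By the normal approximation, n per arm = 2 × (0.7/0.5)² × (1.960 + 0.842)² = 30.8, so 31 per arm and 62 in all. The t-based calculation gives 31.76, so 32 per arm and 64 in all, with power 80.3%. The stated 64 reproduces.

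**Inputs for the illustration**
- Entrants: 32, the planned study-phase completers per arm (SAP 6.2). That all of them enter is an assumption.
- SD of the Visit 8 to Visit 13 change: 0.7 (assumption, borrowed from the study-phase sizing), with range 0.5 to 0.83. The upper end is the source-study SD in SAP 6.2.
- Margin: 0.3 (SAP 7.5.2).
- Level: two-sided 0.05 (SAP 7.2), read as one-sided 0.025.
- Entrants without Visit 13: d = 2, 3 or 5 (assumption). The only documented 6-month rate, 7.5%, belongs to the study phase; 0.075 × 32 = 2.4.
- Gap g: how much worse the change is in leavers than in completers: 0, 0.5 or 1.0 HbA1c points (assumption).

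**Step 1: bias of the completer mean.** Bias = (d/32) × g. With g = 1.0:
- d = 2: 0.0625, or 21% of the margin (0.0625/0.3)
- d = 3: 0.094, or 31%
- d = 5: 0.156, or 52%

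**Step 2: false non-inferiority rate.** Set the mean change over all entrants at exactly 0.3, so that the null hypothesis is true. The completer mean is then 0.3 − bias, with n = 32 − d. Non-inferiority is declared when (observed mean − 0.3)/(0.7/√n) falls below −t(0.975, n − 1). The statistic is noncentral t with noncentrality −bias/(0.7/√n). For d = 2 and g = 1.0 this is −0.0625/(0.7/√30) = −0.49.

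| Leavers of 32 | g = 0 | g = 0.5 | g = 1.0 | g = 1.0, SD 0.5 to 0.83 |
|---|---|---|---|---|
| 2 | 2.5% | 4.2% | 6.9% | 9.7% to 5.9% |
| 3 | 2.5% | 5.4% | 10.3% | 16.2% to 8.5% |
| 5 | 2.5% | 8.1% | 20.0% | 34.6% to 15.4% |

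If the p < 0.05 rule in SAP 7.5.2 were read as one-sided 0.05, the nominal rate would be 5%. The g = 1.0, SD 0.7 column would then read 12.2%, 17.3% and 30.3%.

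**Step 3: no gap.** With g = 0 there is no bias. Power at a true change of zero falls from 65% (all 32 analysed) to 62%, 61% and 57% for 2, 3 and 5 leavers. That works against non-inferiority.

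**Step 4: can such a shift change the conclusion?** The largest observed mean that passes is 0.3 − t × SD/√n. At SD 0.7 this is 0.034 with 29 completers and 0.048 with all 32. A completer mean of 0.00 passes. Add three leavers who are 1.0 point worse and the all-entrant mean is 0.094, which does not.

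**The case against.** Several objections stand.

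- **Direction.** A reader might infer that the plan favours non-inferiority outright. The documents do not support that: they give no dropout rate, reason or pattern for this phase. The direction is conditional, and with no gap the only effect is lower power.
- **Scope.** A reader might also infer that the whole long-term comparison is completer-only. It is not. The treatment group's sensor-glucose endpoints use whatever data a subject has in each 6-month period (SAP 7.9.2.2), so someone who leaves midway can still contribute. The point is confined to HbA1c. Nor does stopping AHCL by itself remove anyone: a subject who stops but has a Visit 13 sample is analysed.
- **Early-termination HbA1c.** The SAP does not exclude it; it leaves its use unstated.
- **The obvious repair.** Putting an early-termination value in the Visit 13 position would act as last observation carried forward. Visit 9 is 14 days after Visit 8, so a subject leaving soon after it would supply a value taken only weeks after Visit 8. That value would tend to show little change and pull the mean towards zero.
- **Existing safeguards.** SAP 7.1.1 reports entrants, completers, early terminations and reasons, and SAP 7.2 reports n. The loss would be visible, though its effect on the test would not be assessed.
- **Status.** The analyses are declared exploratory, and the 6-month confirmatory HbA1c analysis is untouched. This lowers the severity. It does not remove the point, since the SAP still sets a margin, runs a gatekeeping sequence and words its aim as confirmation.
- **Protocol match.** The protocol's 12-month endpoint runs from baseline, whereas the SAP's contrast runs from Visit 8. The mixed-model sentence in 13.6 applies to repeated-measures endpoints in general, so the departure is one of method rather than of a named contrast.

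**Conclusion.** The point holds, at minor severity. The treatment-group HbA1c test is in effect a completer analysis under an ITT label. It uses a method other than the protocol's mixed model, and no sensitivity analysis covers a missing Visit 13.

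The consequence depends on who leaves. If leavers change as completers do, type I error stays at 2.5% and a few points of power are lost. If they do 1.0 point worse, the rate is about three to eight times nominal for 2 to 5 leavers of 32. If they do 0.5 worse, it is 4.2% to 8.1%. These figures rest on assumed entrants, SD, numbers leaving and gap, and on the t test; the Wilcoxon alternative was not computed. They show what the plan is exposed to, not what will happen.

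**What to change.** In SAP 7.2, 7.4 and 7.9.2.1, and in 7.9.1.1 for consistency:

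1. Make the main HbA1c analysis, within each arm and cohort, a linear mixed model on all HbA1c values (Visits 1, 7A, 8 and 13), with the Visit 13 minus Visit 8 contrast. This keeps leavers' earlier values and removes the bias when dropout depends on observed HbA1c.
2. Include an early-termination HbA1c at its actual sampling time, with time modelled so that this is possible. Do not substitute it for Visit 13.
3. Keep the completer paired test as a sensitivity analysis, and report its n beside the ITT n.
4. For the treatment-group non-inferiority test, add a tipping-point analysis: worsen the missing Visit 13 values step by step and report the penalty at which the 0.3% conclusion is lost. This is needed because the mixed model assumes missing at random and cannot by itself answer the concern about leavers doing worse for unobserved reasons.

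The cost is SAP wording and a small amount of programming on data already being collected. The estimate may come out slightly less favourable.

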7.5 Adjustments for Multiple Comparisons

7.5.1 Exploratory Analysis for Control group

The following hierarchical test procedure reflects the relative importance of the endpoints and controls for multiplicity.

Fixed sequential testing of primary and selected secondary endpoints

For the following endpoints, the procedure test hierarchically the ordered hypotheses in sequence at level $\alpha=0.05$ until a first hypothesis is non-rejected.

Primary endpoint

1. Change in HbA1c

Change in HbA1c will be tested for superiority as described in section 7.9.1.1 and a p-value < 0.05 will be considered statistically significant. If p-value < 0.05 , continue to next test, else stop.

Secondary endpoints

2. Percentage of time spent in hyperglycemic range with SG > 250 mg/dL

Non-inferiority test with non-inferiority margin of 6%, if p-value < 0.05 reject null hypothesis and continue, else stop

3. Percentage of time spent in hyperglycemic range with SG > 250 mg/dL

Superiority test, if p-value < 0.05 reject null hypothesis and continue, else stop

4. Percentage of time spent in hyperglycemic range with SG > 180 mg/dL

Non-inferiority test with non-inferiority margin of 6%, if p-value < 0.05 reject null hypothesis and continue, else stop

5. Percentage of time spent in hyperglycemic range with SG > 180 mg/dL

Superiority test, if p-value < 0.05 reject null hypothesis and continue, else stop

6. Percentage of time spent within range 70 - 180 mg/dL

Non-inferiority test with non-inferiority margin of 6%, if p-value < 0.05 reject null hypothesis and continue, else stop

7. Percentage of time spent within range 70 - 180 mg/dL

Superiority test, if p-value < 0.05 reject null hypothesis and continue, else stop

8. Percentage of time spent in hypoglycemic range with SG < 54 mg/dL

Non-inferiority test with non-inferiority margin of 2 %, if p-value < 0.05 reject null hypothesis and continue, else stop

9. Percentage of time spent in hypoglycemic range with SG < 70 mg/dL

Non-inferiority test with non-inferiority margin of 5 %, if p-value < 0.05 reject null hypothesis and continue, else stop

Additional analysis

Superiority test for percentage of time spent in hypoglycemic range with SG < 54 mg/dL, < 70 mg/dL and

analyses on ancillary endpoints and safety endpoints may be performed, and p-values will be reported but may not be claimed.

7.5.2 Exploratory Analysis for Treatment Group

The following hierarchical test procedure reflects the relative importance of the endpoints and controls for multiplicity.

Fixed sequential testing of primary and selected secondary endpoints

For the following endpoints, the procedure test hierarchically the ordered hypotheses in sequence at level $\alpha=0.05$ until a first hypothesis is non-rejected.

Primary endpoint

1. Change in HbA1c

Change in HbA1c will be tested using a non-inferiority test with margin of 0.3%, as described in section 7.9.1 and a p-value < 0.05 will be considered statistically significant. If p-value < 0.05 , continue to next test, else stop.

Secondary endpoints

2. Percentage of time spent in hyperglycemic range with SG > 250 mg/dL

Non-inferiority test with non-inferiority margin of 6%, if p-value < 0.05 reject null hypothesis and continue, else stop

3. Percentage of time spent in hyperglycemic range with SG > 180 mg/dL

Non-inferiority test with non-inferiority margin of 6%, if p-value < 0.05 reject null hypothesis and continue, else stop

4. Percentage of time spent within range 70 - 180 mg/dL

Non-inferiority test with non-inferiority margin of 6%, if p-value < 0.05 reject null hypothesis and continue, else stop

5. Percentage of time spent in hypoglycemic range with SG < 54 mg/dL

Non-inferiority test with non-inferiority margin of 2 %, if p-value < 0.05 reject null hypothesis and continue, else stop

6. Percentage of time spent in hypoglycemic range with SG < 70 mg/dL

Non-inferiority test with non-inferiority margin of 5 %, if p-value < 0.05 reject null hypothesis and continue, else stop

Additional analysis

Analyses on ancillary endpoints and safety endpoints may be performed, and p-values will be reported but may not be claimed.

7.6 Demographic and Other Baseline Characteristics

A summary of basic subject demographics, medical history and other baseline characteristics will be reported using appropriate summary statistics (number of subjects (n), mean, standard deviation, median, minimum and maximum for continuous variables; frequency and percentages for categorical variables). Baseline summary for all subjects and by treatment group will be presented.

Demographics, medical history and other baseline characteristics will be obtained from eCRF and baseline sensor data. Baseline variables to be summarized include, but are not limited to: age, sex, weight, BMI, country of enrollment, HbA1c, Diabetes history, Creatinine Clearance value and total insulin dose per day.

7.7 Treatment Characteristics

Not applicable.

7.8 Interim Analyses

Not applicable for continuation phase.

7.9 Evaluation of Objectives

7.9.1 Exploratory Analysis for Control group

7.9.1.1 Primary Endpoints: Mean HbA1c

As the control group switched to AHCL therapy during the continuation phase, the goal is to compare the mean HbA1c from the end of study phase (6 months) to the end of continuation phase (12 months) within control group (MDI+FGM). The within group difference in the mean HbA1c is of primary interest and will be compared using the following hypotheses:

Null-hypothesis: $H_0: HbA1c_{\text{study period}} = HbA1c_{\text{continuation phase}}$

Alternative hypothesis: $H_a: HbA1c_{\text{study period}} \neq HbA1c_{\text{continuation phase}}$

Where $HbA1c_{\text{study period}}$ is the mean HbA1c (6 months [Visit 8]) of the control group, and $HbA1c_{\text{continuation phase}}$ is the mean HbA1c (12 months [Visit 13]) of the control group. The null hypothesis will be tested against the alternative hypothesis using paired t test if normality assumption is met, Wilcoxon signed rank test if normality assumption is rejected. Superiority of AHCL will be concluded if $HbA1c_{\text{study period}} > HbA1c_{\text{continuation phase}}$.

7.9.1.2 Secondary Endpoints

The blinded (for study period) or unblinded (for continuation phase) sensor data collected during the 2 periods of 2 weeks (at 3 months and 6 months for the study phase, and at 9 month and 12 month in the continuation phase) will be combined and then used to perform all statistical test mentioned below. Descriptive summaries of all outcomes mentioned below generated with all 6 month SG data in continuation phase will be provided as well.

7.9.1.2.1 Percentage of Time in Range (70-180 mg/dL), in Hyperglycemia (> 180 mg/dL, > 250 mg/dL) and Hypoglycemia (< 54 mg/dL, < 70 mg/dL)

Percentage of time spent within range with sensor glucose (SG) between 70 - 180 mg/dL (3.9-10.0 mmol/L), in hyperglycemic range with SG > 180 mg/dL (> 10.0 mmol/L), > 250 mg/dL (13.9 mmol/L) and in hypoglycemic range with SG < 54 mg/dL (3.0 mmol/L), < 70 mg/dL (3.9 mmol/L) will be computed using the sensor data collected during each of the 2 periods of 2 weeks. The last 8064 sensor readings (4 weeks) from each period will be used for analysis.

The percentage of time spent within range (70-180 mg/dL) for subject i at period j will be calculated as:

$$\frac{\text{Total number of sensor reading with SG between } 70 - 180 \text{ mg/dL for subject i at period j}}{\text{Total number of sensor readings for subject i at period j}}$$

The percentage of time spent in hyperglycemic range > 180 mg/dL or > 250 mg/dL for subject i at period j will be calculated as:

$$\frac{\text{Total number of sensor reading with SG } > 180 \text{ or } > 250 \text{ mg/dL for subject i at period j}}{\text{Total number of sensor readings for subject i at period j}}$$

Similarly, the percentage of time spent in hypoglycemic range < 54 mg/dL or < 70 mg/dL for subject i at period j will be calculated as:

$$\frac{\text{Total number of sensor reading with SG } < 54 \text{ or } < 70 \text{ mg/dL for subject i at period j}}{\text{Total number of sensor readings for subject i at period j}}$$

The within group difference of Time in specific range (70-180, <54, <70, >180, >250 mg/dL) between study period and continuation phase will be compared using paired t test if normality assumption is met, Wilcoxon signed rank test if normality assumption is rejected.

7.9.1.3 Ancillary Endpoints

The blinded (for study period) or unblinded (for continuation phase) sensor data collected during the 2 periods of 2 weeks (at 3 months and 6 months for the study phase, and at 9 month and 12 month in the continuation phase) will be combined and then used to perform all statistical test mentioned below. Descriptive summaries of all outcomes mentioned below generated with all 6 month SG data in continuation phase will be provided as well.

Superiority test will be applied to ancillary endpoints if needed.

7.9.1.3.1 Number of Biochemical Hypoglycemic events

A biochemical hypoglycemic event with SG < 54 mg/dL is defined as sensor glucose values less than 54 mg/dL (3.0 mmol/L) for 15 or more consecutive minutes. A biochemical hypoglycemic event with SG < 70 mg/dL is defined as sensor glucose values less than 70 mg/dL (3.9 mmol/L) for more than 20 consecutive minutes. When the time between two successive events is less than 30 minutes, they will be combined and counted as one event. The mean number of biochemical hypoglycemic events with SG < 54 mg/dL (3.0 mmol/L), < 70 mg/dL (3.9 mmol/L) per subject per week based on 15 and 20 consecutive minutes will be computed using the sensor data collected during each of the 2 periods of 2 weeks. The last 4032 sensor readings (2 weeks) from each period will be used for analysis. The mean number of hypoglycemic events (MNHE) per week at each period for each subject will be calculated as:

$$\frac{\text{number of biochemical hypoglycemic event for subject } i \text{ at period } j}{\text{duration of sensor wear for subject } i \text{ at period } j \text{ in weeks}}$$

Where the duration of sensor wear for subject *i* at period *j* is the number of sensor readings (capped at 4032) for subject *i* at period *j* divided by 2016. Mean number of biochemical hypoglycemic events with SG < 54 mg/dL (3.0 mmol/L) based on 20 minutes definition and < 70 mg/dL (3.9 mmol/L) per week based on 15 minutes definition will be analyzed and reported as additional analyses. Analysis on mean number of biochemical hypoglycemic events with SG < 54 mg/dL (3.0 mmol/L) (based on 15 minutes) will be using non-inferiority test with non-inferiority margin of 35% of the observed mean in the control group.

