5.2 Randomization

If subjects meet the inclusion and exclusion criteria, as well as all the following criteria assessed at the end of the run-in period, they may continue to participate in the study phase:

1. Subject has worn the sensor with blinded transmitter during the run-in period adequately, per investigator judgment.
2. Subject has shown acceptable tolerance to sensor wear, per investigator judgment.
3. CareLink data shows subject performed ≥ 2 finger stick blood glucose measurements daily, as determined by CareLink data upload as the mean number of SMBG/day over the past 14 days.
4. Subject has shown compliance with study procedures, per investigator judgment.

Subjects in each cohort will be randomized into 2 arms at the end of the run-in phase:

Cohort A (confirmatory): Subjects on **MDI + FGM** will be randomized into:

- Treatment Arm: Start AHCL (and stop FGM at visit 6A)
- Control Arm: Continue MDI + FGM

Cohort B (exploratory): Subjects on **MDI + Real-Time CGM** will be randomized into:

- Treatment Arm: Start AHCL (and stop CGM at visit 6A)
- Control Arm: Continue MDI + CGM

Each cohort will have a separate randomization.

6. Determination of Sample Size

Subjects entered the continuation phase after completed the study period. All subjects with data in the continuation phase will be included in the analysis. No power analysis has been done for this exploratory phase of the study. All analysis in this document is exploratory.

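### The 35% hypoglycaemic-event margin is estimated from the same control subjects it is applied to, its reference phase is not named, and the paired test leaves out its sampling error

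*SAP*

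**What the plan says.** SAP 7.9.1.3.1 analyses the control group's weekly rate of events below 54 mg/dL (15-minute definition) by a "non-inferiority test with non-inferiority margin of 35% of the observed mean in the control group". It limits the data to the last 4032 readings per period, which is 4032/2016 = 2 weeks.

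The method comes from SAP 7.2: "Comparisons between the study phase and the continuation phase will be performed using a paired T-test", with the Wilcoxon signed rank test if normality is not met. The same section says "The data from control group and treatment group will be evaluated independently for all endpoints" and "P-values for hypothesis testing will be evaluated based on two-sided testing using significance level of 0.05". No other procedure is given for this margin.

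Three other places matter:
- SAP 7.9.1.3, which introduces the control group's ancillary endpoints, provides for superiority testing where needed and does not mention non-inferiority.
- SAP 7.9.2.3.1 repeats the margin sentence word for word for the treatment group.
- SAP 7.5.1 leaves ancillary endpoints out of the fixed sequence. Their p-values are to be reported but are not a basis for claims.

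**The concern.** There are two separate problems.

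**The reference is undefined.** The control group has an MDI mean from the study phase and an AHCL mean from the continuation phase. Two programmers could pick different ones and reach different conclusions from the same data. If the AHCL mean sets the margin, more events on AHCL make the margin wider.

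**The margin is an estimate.** A margin taken from the sample moves with the sample. A paired t-test of the phase difference against it counts the variation in the difference and omits the variation in the margin. With the study-phase mean, the resulting confidence limit is generally too tight, in the direction that favours AHCL.

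At stake is a reported p-value on a safety-relevant outcome. The SAP's hypoglycaemia tests within the fixed sequence (time below 54 and below 70 mg/dL) use absolute margins of 2% and 5% and are not affected.

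**Working it through.** **Inputs from the documents.** The margin is 35% of an observed mean. A two-sided 0.05 level is one-sided 0.025 when non-inferiority is read from a 95% interval. The control group size follows from "the minimum sample size required is 64 subjects (32 in each arm) in Cohort A". The SAP gives no event rate, SD, within-subject correlation or power for this test; those below are assumptions.

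**Reproducing the plan's own figure.** The stated inputs are "alpha=0.05, power=80%, 0.7 standard deviation and 0.5 reduction in mean change of HbA1c in the treatment arm". The normal formula gives 2 x (1.960 + 0.842)² x 0.7²/0.5² = 30.8, so 31 per arm. The t-based calculation gives 31.76, so 32 per arm and 64 in total, as stated. I therefore use 32 pairs.

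**Reading 1: study-phase mean.** Let X1 be the study-phase rate and X2 the continuation rate. Non-inferiority is declared when mean(X2 - X1) - 0.35 x mean(X1) is far enough below zero. That quantity is mean(X2 - 1.35 X1), but the standard error used is that of mean(X2 - X1). At a true ratio of exactly 1.35, the large-sample false non-inferiority rate is

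1 - Φ(1.96 x SD(X2 - X1) / SD(X2 - 1.35 X1)),

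which does not depend on n. With SD(X1) = 1:

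| SD of X2 | Correlation | SD(X2 - X1) | SD(X2 - 1.35 X1) | False non-inferiority |
|---|---|---|---|---|
| 1 (equal) | 0 | 1.414 | 1.680 | 5.0% |
| 1 (equal) | 0.8 | 0.632 | 0.814 | 6.4% |
| √1.35 | 0 | 1.533 | 1.781 | 4.6% |
| 1.35 (proportional) | 0 | 1.680 | 1.909 | 4.2% |
| 1.35 (proportional) | 0.8 | 0.814 | 0.854 | 3.1% |

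That is 3.1/2.5 = 1.2 to 6.4/2.5 = 2.6 times nominal for correlations of 0 to 0.8. At correlation 0.9 the range widens to 2.1% (proportional SD, no inflation) up to 8.1% (equal SD). At one-sided 0.05 the corresponding rates for correlations of 0 to 0.8 are 5.8-7.4% (proportional SD) and 8.3-10.1% (equal SD), or 1.2-2.0 times nominal.

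**Simulation with skewed counts.** The assumptions are 32 pairs, 1.5 events per week on MDI, between-subject CV 0.6-1.0, correlation 0.3-0.7, lognormal subject rates with Poisson counts, a true ratio of 1.35 and the paired t-test.
- Estimated margin: about 4.7-5.6% with 4 weeks of data and 4.6-5.5% with the SAP's 2-week cap.
- Known margin of 0.35 x 1.5 = 0.525: about 3.0-4.4%. This excess over 2.5% comes from skewness alone, so the estimated margin itself adds a factor of about 1.3-1.6.
- Standard error too small by a factor of about 1.12-1.15.
- Paired t-test on X2 - 1.35 X1: 2.1-2.5%.

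**Wilcoxon fallback.** With 1 event per week, 4 weeks of data, CV 0.7-1.5 and correlation 0-0.8, the estimated margin gives 7.0-16.2% and a known margin 3.1-10.2%. The signed rank test applied to X2 - 1.35 X1 gives 2.1-2.6%.

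**Reading 2: continuation mean.** The rule becomes X2 - X1 < 0.35 X2, or 0.65 X2 < X1, so the tolerated ratio is 1/0.65 = 1.54. Against that limit the test is not inflated over correlations 0 to 0.8. With equal SDs, for example, the rate is 1 - Φ(1.96 x 1.414/1.193) = 1.0% at correlation 0, and 2.3% at 0.8.

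**The case against.** Three stronger readings are tempting, and the documents do not support them.

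1. *The rule doubles the false non-inferiority rate.* The doubling appears with equal SDs at one-sided 0.025, or when the skewness error is counted in. It shrinks to about 1.2-1.8 times if the SD rises with the mean, and there is no inflation if the continuation mean is meant. The SAP gives none of the quantities that would settle this, so only a range with stated assumptions is defensible.
2. *The SAP orders the margin to be treated as a constant.* It never says so. That follows from its naming only a paired t-test or signed rank test and giving no method for the margin's variance.
3. *A hypoglycaemia claim is at risk.* The endpoint is ancillary, all analyses in this SAP are exploratory, and SAP 7.5.1 already rules out a claim from these p-values.

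The case for leaving the text alone rests mainly on the third point, and it stands as far as severity goes. It does not make the rule executable, because the reference phase is still missing and the result is still to be reported with a p-value. It is also fair that the Wilcoxon figures rest on more skewed assumed data and that part of their excess is present with a known margin.

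**Conclusion.** The point holds as a minor one. The missing reference phase needs no assumption about the data: the tolerated ratio is 1.35 under one reading and 1.54 under the other. The understated standard error applies to the study-phase reading. With 32 pairs and the assumed rates, false non-inferiority is about 4.7-5.6% against 2.5%, of which the estimated margin accounts for a factor of about 1.3-1.6. Over the wider set of SDs and correlations (0 to 0.8) considered for the t-test, the total is about 1.2-2.6 times nominal. The treatment-group copy of the sentence has a further fault: it refers to the control group in a comparison that, under SAP 7.2, contains no control-group data.

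**What to change.** In SAP 7.9.1.3.1, name the control group's study-phase mean as the reference and state the hypothesis as a ratio: non-inferior if the continuation rate is below 1.35 times the study-phase rate. Prespecify one method: a paired test on each subject's continuation rate minus 1.35 times the study-phase rate, using the section's 2-week window. If the signed rank fallback is kept, apply it to the same contrast. A log-link count model with a wear-time offset is a different analysis, since it weights subjects differently and works on the log scale, so it should not be left as an interchangeable option.

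Amend the identical sentence in SAP 7.9.2.3.1 so that the reference mean belongs to the comparison being made. Reconcile SAP 7.9.1.3, which mentions only superiority testing, with the non-inferiority test beneath it.

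The cost is a few sentences and no new data; the sponsor's 35% tolerance is kept. The chance of showing non-inferiority falls because an omitted source of error is now counted. At truly equal rates with the 2-week window, it drops from about 31-53% to 19-39% under the simulation assumptions. No planned power is lost, because the SAP's sample size section says "No power analysis has been done for this exploratory phase of the study".
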